#### **1.4.2.2. Renal-Related Results**

No REACT delivery-related macroscopic or microscopic findings were observed at the one- or 3-month endpoint. No treatment-related kidney findings were noted following enhanced evaluation of 8 areas of each kidney (3 stains per area), including evaluation and scoring of 150 glomeruli per kidney. Apart from changes related to injection site scars all kidneys were normal. All macroscopic and microscopic kidney changes were considered background findings or related to the injection procedures.

#### **1.4.2.3. Non-Renal Findings**

No test article-related findings were identified in other (non-kidney) tissues. All macroscopic and microscopic changes were considered background changes and within normal limits.

#### 1.4.2.4. Procedure-Related Findings

The most common abnormalities included swelling at the incision sites (seroma formation) and weight loss at study termination. With regard to incision site swelling, ten of sixteen (10/16) animals had sterile seroma formation post-implantation, and nine of sixteen (9/16) post treatment. The animals had varying degrees of swelling at their retroperitoneal incisions and were treated as deemed necessary by a veterinarian.

Numerous animals had mild inappetence following REACT administration (29 of 32) and treatment procedures (18 of 32). Most animals (28 of 32) experienced weight loss from baseline (prior to implantation) to termination. Of note, a greater amount of weight loss occurred between baseline (2 weeks prior to treatment) and treatment (Day 0; renal injections) than between treatment and termination. Weight loss also occurred across all treatment groups and was judged to be related to the stressful nature of the study.

#### 1.4.2.5. Conclusions

- All animals survived to their designated termination time point and were in good general health throughout the study based on clinical pathology, urinalysis, and veterinary assessment.
- Neither the low or high dose of REACT produced macroscopic or microscopic adverse effects at one- or 3-months post-treatment, similar to observations following sham treatment or treatment with the biomaterial.
- Pathological evaluation showed no REACT safety-related (macroscopic or microscopic) findings in the target (kidney) or non-target organs examined.
- Based on anatomic pathology, the observed NOAEL was the higher concentration tested, i.e.,  $11.7 \times 10^6$  cells/g KWest.

### 1.4.3. Repeat Dose Canine Study

The second canine toxicology study assessed the safety of administering two repeat doses of REACT. Each dose was delivered into both kidneys at baseline (time zero) and 3 months. All animals were subjected to two renal biopsies per kidney 4 to 6 weeks prior to the baseline injection procedure. Control animals were injected with PBS. Animals were monitored for 6 months following the baseline injection.

#### 1.4.3.1. Study Results

All 8 animals were in good clinical health throughout the study and survived to their designated termination time point at 6 months. There was mild or insignificant weight loss in 5 of 8 animals, with 2 animals losing >3% body weight for the duration of the study. Greater weight loss occurred between the renal implantation and initial treatment than between the initial treatment and termination. The clinical pathology and urinalysis data revealed no abnormal trends. There were no signs of renal insufficiency, and no indications of decreased GFR.

#### 1.4.3.2. Kidney-Related Findings

No REACT implantation safety-related macroscopic or microscopic findings were observed at the 6-month time point. No treatment-related kidney findings were noted following enhanced evaluation of 8 areas of each kidney (3 stains per area), including evaluation and scoring of 150 glomeruli per kidney. All kidneys appeared normal, apart from changes related to injection site

scars (fibrosis/chronic inflammation in the capsule; linear fibrosis/chronic inflammation and inflammatory cells in the cortex/medulla).

#### **1.4.3.3. Non-Kidney Related Findings**

No test article safety-related findings were identified in non-target tissues. All macroscopic and microscopic changes were considered background changes and thus, considered within normal limits.

#### **1.4.3.4. Conclusions**

- All animals survived to their designated termination time point, and appeared in good health based on clinical pathology, urinalysis, and veterinary assessment data.
- Pathological assessment showed no REACT safety-related (macroscopic or microscopic) findings in either the target organ (kidney) or non-target organs examined.
- At the 6-month time point, no detrimental effects of two repeat doses of REACT were observed in comparison to the control animals injected with PBS.

### **1.5. Non-clinical Conclusions**

Evidence from multiple animal studies over a wide range of doses (3 to 15 million SRC/g of kidney tissue implanted), and extended periods of time post-REACT treatment (up to one year), including three GLP studies, indicates that the potential risk of complications from REACT delivery into the kidney is similar to the potential risk of complications associated with standard renal biopsy practice.

Apart from changes related to injection procedures and cardiovascular findings specific to 5/6th nephrectomy rodent mass reduction model of CKD, no unanticipated in-life, hematological, urological, serological, or histological changes were found in the target organ or non-target tissues following delivery of REACT.

### **1.6. Phase 1 Clinical Trial: Interim Results**

#### **1.6.1. Background**

In April 2013, a first-in-human clinical trial was initiated at the Karolinska University Hospital Huddinge in Stockholm, Sweden: A Phase 1, Open-Label Safety and Delivery Optimization Study of Renal Autologous Cell Therapy (REACT) in Patients with Chronic Kidney Disease (RMTX-CL001). This is a Phase 1, open-label, safety and delivery optimization study of REACT implanted into subjects with CKD. REACT will be manufactured from SRC obtained from a subject's renal biopsy, formulated with gelatin biomaterial, and injected back into the subject's left kidney. The primary objective is to assess the safety and optimal delivery of REACT implanted at one site in a recipient kidney as measured by procedure- and/or product-related adverse events (AEs) through 12 months post-treatment. The secondary objective is to assess renal function by comparing the results of laboratory tests from baseline through 12 months following REACT injection, followed by an additional observational period of 18 months. Each subject's baseline rate of CKD disease progression serves as his/her own "control" to monitor for changes in renal insufficiency over time. Six subjects, recruited from the Karolinska University Hospital, were enrolled into the study. In addition, one subject was enrolled in the study at the University of North Carolina.

#### 1.6.4. Serum Creatinine

[figure not shown]
Pre-treatment levels of serum creatinine (sCr) were generally elevated in this cohort, which would be expected from subjects with T2DM and moderate to severe renal insufficiency (Stage 3b/4 of

CKD). The annual rate of change for sCr, before and after REACT treatment, is presented for each subject in Table 8. All subjects demonstrated a reduction in their individual rate of increase for sCr following REACT treatment compared to the rate of sCr increase that had been observed before REACT treatment.

**Figure 2: Serum Creatinine Pre- and Post-REACT Treatment (RMTX-CL001)**

### 1.5.1. Kidney Cortical Thickness

Patients suffering from chronic kidney disease undergo a thinning of the functional portion of the kidney, i.e., the cortex. Renal cortical thickness is reduced in CKD as a result of fibrosis and

scarring as the disease progresses. An increase in cortical thickness was associated with kidney regeneration in pre-clinical studies of REACT and was confirmed histologically in all 4 animal species studied (refer to the [Investigator's Brochure](#)). In the clinical trials TNG-CL010 and TNG-CL011, cortical thickness was evaluated using imaging technologies; no biopsies were taken to confirm the basis for the increased thickness. Cortical thickness was measured in both the right and left kidney to determine if the implanted left kidney exhibited any change in cortical thickness that could be attributed to REACT implantation. The right kidney served as a non-implanted control.

On average, cortical thickness increased in the left kidney from 14 mm at baseline to approximately 16 mm after one year of REACT treatment. This change in cortical thickness was not sufficient to cause an increase in the total volume of the left kidney (data not presented). No change in cortical thickness was observed in the right kidney cortex.

#### **1.6.5. Hemoglobin**

CKD can be associated with anemia due to an alteration in renal erythropoietin production as well as metabolic abnormalities resulting from chronic uremia. In the clinical trial RMTX- CL001, 3 of 7 subjects exhibited improvement in hemoglobin levels after REACT treatment, while the remaining 4 subjects maintained normal levels during the study.

#### **1.6.6. Blood Pressure**

Blood pressure was monitored during the course of clinical trials TNG-CL010 and TNG-CL011. Subjects received medication to control their blood pressure. Notably, intake of antihypertensive medication was reduced in 3 of 6 subjects during the first six months following REACT treatment.

### **1.7. Potential Risks**

In general, potential risks associated with the clinical use of REACT can be broadly divided into 3 categories: kidney biopsy, REACT product, and delivery into the recipient kidney. An assessment of potential risks associated with each of these steps is presented in this Section.

At this time, there are no specific warnings or precautions associated with the use of REACT. However, warnings and precautions for the renal biopsy and the percutaneous injection procedure must be considered with use of this product. The risks of renal biopsy have been well characterized in the 100 years that this procedure has been used and developed. Percutaneous needle instrumentation of the kidney has a shorter history.

The risks of renal biopsy and percutaneous needle kidney injection include:

1. Pain in flank / injection/biopsy site
2. Bleeding at injection/biopsy site which may occur around the kidney or anywhere along the needle track and which may be sufficient to entail clinically significant anemia, acute kidney injury (AKI), hematoma, and in the case of subcapsular bleeding, a “Page kidney” and acute hypertension
3. Surgical damage to the kidney from needle injury, as well as injuries of other structures that include connective tissues, bone, and intra-abdominal viscera

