#### **1.7.1. Potential Risks Associated with Renal Biopsy**

Autologous kidney cells will be obtained from individual subjects via a kidney biopsy performed according to standard medical practice and consistent with standard operating procedures at participating hospitals /medical institutions. A minimum of 2 tissue cores from a single kidney

biopsy is needed to obtain sufficient renal cortical tissue for the production of REACT. A 16-gauge biopsy needle measuring approximately 10 mm in length will remove 0.01-0.02% of the average total volume of the diseased kidney. Since approximately 0.001% of the total number of renal glomeruli will be harvested, the biopsy is not expected to adversely affect kidney function.

Kidney biopsies for diagnostic procedures are of low risk and often conducted under sedation on an outpatient basis in the US. When performed by qualified interventional physicians, a renal biopsy properly targeted towards the cortex produces limited renal damage. On the other hand, reports of kidney damage at the biopsy site describe vascular injury and varying degrees of ischemia and infarction. The severity of damage depends on the size and number of vessels injured during the biopsy procedure.

Hemorrhage is the most common AE associated with a routine kidney biopsy. Nearly all patients experience microscopic hematuria as a result of the biopsy, but this is not clinically significant. On the other hand, gross hematuria occurs in 3-9% of patients, and generally resolves by 24 hr. post-biopsy. The most serious complication is severe bleeding that requires transfusion and/or results in patient death. Transfusions are needed in less than 1% of renal biopsies, and death occurs in less than 0.01% of cases.

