### 7.3.3. Hematology

Hemorrhage following biopsy and REACT injection is a known and foreseeable risk to subjects participating in this study. Therefore, hemoglobin and hematocrit will be measured by the site's local laboratory before and after each procedure and compared to baseline levels. Other bleeding parameters (e.g., APTT, PTT-INR, platelets) also will be measured throughout the study.

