#### **8.1.1.2. Other Significant Adverse Events**

Significant events of particular clinical importance include SAEs and AEs leading to premature discontinuation of subjects from the study. These events will be recorded in the subjects' medical records as well as the CRF provided by the Sponsor or its designee. Narratives of these events may be prepared for inclusion in the Clinical Study Report.

The following sections describe "adverse events of special interest" concerning procedure- and product-related events. Subjects should be carefully monitored for the occurrence of these potential AEs.

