#### **8.1.1.3. Procedure-Related Events**

**Post-procedure pain:** If the subject experiences pain following the biopsy or REACT injection, administration of paracetamol or paracetamol-codeine combinations is recommended. More severe pain in the loin or abdomen requires ultrasonography to exclude significant perirenal hemorrhage. If severe pain occurs, administration of opiates may be necessary. If analgesic doses higher than the maximum authorized doses are required to alleviate pain, then the Investigator must perform additional clinical evaluations to ascertain the probable cause(s) of excessive pain.

**Hemorrhage:** Following renal biopsy and REACT injection procedures, subjects undergo regular hemoglobin and blood pressure monitoring. Subjects will be confined to bed and monitored for maintenance of normal coagulation indices. If bleeding occurs and the subject is hypotensive despite bed rest, a blood transfusion may be considered. If the bleeding is still not controlled, surgery may be considered. In rare cases, renal angiography may be performed to identify the source of bleeding. Coil embolization can be performed during the same procedure.

**Other complications:** In very rare cases, other organs (such as liver, gallbladder and lungs) may be penetrated during the biopsy procedure. In these cases, appropriate treatment and follow- up may be discussed with consulting surgeons.

**Death:** Deaths resulting from renal biopsies occur in <0.01% of patients. Adherence to strict inclusion /exclusion criteria will ensure that subjects who may be predisposed to uncontrolled or excessive bleeding will not be enrolled in this trial.

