- k. the number and percentage of subjects experiencing a TEAE leading to study discontinuation during the acute first injection, inter-injection, acute second injection, post-second injection, and post-injection periods
- l. the number and percentage of subjects experiencing a TEAE leading to death during the acute first injection, inter-injection, acute second injection, post-second injection, and post-injection periods

In the overall summary of AEs table, besides tabulating the number and percentage of subjects, the total number of AE episodes will also be provided. If a subject has repeated episodes of a particular AE, all episodes will be counted in the summary table.

Additionally, each of the categories of events presented in the overall summary of AEs table will be summarized by SOC and PT in individual tables. In the remaining summary tables, the incidence of TEAEs will be calculated by dividing the number of subjects who have experienced the event by the total number of subjects in the analysis set. Thus, the incidence of TEAEs is shown in terms of the total number of subjects and not in terms of the total number of episodes. If a subject has repeated episodes of a particular TEAE, only the most severe episode, or the episode with the strongest causal relationship to biopsy, REACT product, or REACT injection procedure will be counted in the summary tables.

A subject with more than one type of TEAE in a particular SOC will be counted only once in the total number of subjects experiencing TEAEs in that particular SOC. Since a subject could have more than one type of TEAE within a particular SOC, the sum of subjects experiencing different TEAEs within the same SOC could appear greater than the total number of subjects experiencing TEAEs in that SOC. Similarly, a subject who has experienced a TEAE in more than one SOC will be counted only once in the total number of subjects experiencing AEs in those SOCs.

All AEs will be presented in tables in descending order from the SOC with the highest incidence to the SOC with the lowest incidence. Within each SOC, AEs will be sorted in descending order from the PT with the highest incidence to the PT with the lowest incidence.

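### Hemorrhage is named in the protocol as an event of special interest, but the SAP gives it no grouped count and no denominator of subjects who had each procedure

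*Protocol*

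**What the plan says.** **Protocol.** Section 1.7 gives one list of risks for the biopsy and the injection, and its second entry starts: "Bleeding at injection/biopsy site which may occur around the kidney or anywhere along the needle track". Section 1.7.1 states: "Hemorrhage is the most common AE associated with a routine kidney biopsy". Section 7.3.3 covers both procedures: "Hemorrhage following biopsy and REACT injection is a known and foreseeable risk to subjects participating in this study". Section 8.1.1.2 introduces the sections that follow it as describing "adverse events of special interest", and 8.1.1.3 then lists post-procedure pain, hemorrhage, other complications and death. The hemorrhage entry begins: "Following renal biopsy and REACT injection procedures, subjects undergo regular hemoglobin and blood pressure monitoring". The primary endpoint (2.1) is AEs related to the procedure or the product, so bleeding is the main expected harm within it.

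**SAP.** Section 7.2.5, items a to l, counts subjects with any AE, by greatest intensity, by relationship (biopsy, product, injection procedure), with an SAE, with an AE leading to discontinuation, and with an AE leading to death. These are given by analysis period. Then "each of the categories of events presented in the overall summary of AEs table will be summarized by SOC and PT in individual tables". Incidence in those further tables is subjects with the event divided by all subjects in the analysis set. There is no bleeding row, term list or special-interest category for AEs. The SAP uses the idea of special interest only for medications (5.5). Its list of differences from the protocol (Section 10) does not mention the point.

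**The concern.** The protocol marks out one harm in advance and asks that subjects be watched closely for it, yet no planned table answers the obvious question: how many subjects bled after the biopsy, after the first injection and after the second?

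Two features of SAP 7.2.5 cause this. First, one kind of needle injury can be coded as hematuria, perirenal hematoma or procedural hemorrhage, and these need not share a PT or an SOC. One level up, in the relationship rows, bleeding is mixed with pain and everything else. Second, the stated denominator is the analysis set and not the subjects who had the procedure. Protocol 4.4 and SAP 3.2.4 both allow the second injection to be withheld, so the two can differ.

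With at most 10 subjects, moving one or two events between rows, or one or two subjects in or out of the denominator, changes the printed percentage noticeably. If the bleeding definition is chosen only after the listings have been read, it can also be shaped by what they show.

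**Working it through.** The plan has no figure to reproduce: the sample size is up to 10, without a calculation, and the analysis is descriptive. The check is a reading of the planned outputs, followed by small illustrations with assumed event counts.

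**1. Which outputs could show a bleed?**
- SAP 7.2.5 items e, f and h: AEs related to biopsy or injection procedure, by period, with episode totals in the overall table. All event types are together.
- SAP 7.2.5 SOC and PT tables: subjects only, not episodes. Bleeding is spread over terms.
- SAP 7.1: numbers of biopsies and injections, not used as a denominator for any AE.
- SAP 7.7: any safety ultrasound abnormality, by visit.
- SAP 6.2 and 7.3: hemoglobin and hematocrit as laboratory values. Protocol 8.3 says a clinically significant laboratory change need not be reported as an AE unless it is serious or leads to discontinuation, so a fall in hemoglobin alone may not reach the AE tables.

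None of these gives subjects with any procedural bleed.

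**2. How many events are likely?** Protocol 1.7.1 says "gross hematuria occurs in 3-9% of patients" after a biopsy. Assume that 3 to 9% applies to each of 10 biopsies and 20 injections, independently.
- Expected events: 30 × 0.03 = 0.9 to 30 × 0.09 = 2.7.
- Chance of at least one: 1 − 0.97^30 = 60% to 1 − 0.91^30 = 94%.

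So about one to three events are expected, a range in which PT rows tend to hold single subjects.

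**3. Effect of splitting.** Assume three of 10 subjects bleed once each, under three PTs.
- PT rows: 1/10 = 10%, three times (exact 95% CI 0.3 to 44.5%).
- Grouped: 3/10 = 30% (6.7 to 65.2%).
- If all three bleeds followed injections and 20 were given: 3/20 = 15% per injection (3.2 to 37.9%).

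The intervals are added here to show the imprecision; the SAP plans none for AEs.

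**4. Effect of the denominator.** Assume one bleed after the second injection.
- SAP rule, 10 subjects in the analysis set: 1/10 = 10.0%.
- Eight subjects received it: 1/8 = 12.5%.
- Six subjects received it: 1/6 = 16.7%.

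**5. Biopsy denominator.** Protocol 5.4 lets subjects biopsied under RMCL-002 enter without a second biopsy. The SAP does not say whether they count as biopsied here. If two of 10 came that way, one biopsy bleed is 1/10 or 1/8, depending on the choice.

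**The case against.** The strongest reply is that the SAP keeps the special-interest class. Protocol 8.1.1.2 describes it as procedure- and product-related events, and SAP 7.2.5 items e to h count those, by period, with episode totals and a separate listing for each category. Three related bleeds in one period would appear together in one of those rows, and PTs that share an SOC are pooled in its total. The protocol asks for careful monitoring and does not promise a hemorrhage table. Protocol 9.7.2 leaves room for further summaries, and with 10 subjects a reader can count bleeds from the listings.

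Most of this stands. A reader might infer that the SAP discards the class or loses the data, and the documents do not support that. What is missing is a bleeding grouping inside a class that is kept. A hand count is possible, but its definition would not be fixed in advance.

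A reader might also blame the analysis periods for fragmenting the signal. They do not: the pre-injection, acute first and acute second injection periods in SAP 4.9 each isolate one procedure. Section 4.9 also says that the post-second-injection period does not apply to subjects with one injection, which could be read as shrinking the denominator. But 7.2.5 states the denominator, and it names the whole analysis set.

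Two further inferences fail. Setting 3/10 against 3 to 9% does not reveal an excess. That range is gross hematuria after one biopsy, whereas the grouped count is broader and covers up to three procedures. Under the same independence assumption, three or more events in 30 procedures have probability 51% at a 9% rate and 6.0% at 3%. Nor does the SAP leave a trial hypothesis untested. Protocol 1.5 does say: "the potential risk of complications from REACT delivery into the kidney is similar to the potential risk of complications associated with standard renal biopsy practice". But this is a conclusion from animal studies, and no hypothesis test is planned.

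**Conclusion.** The point holds as a gap in pre-specified reporting. A harm that the protocol names as of special interest, and that falls within the primary endpoint, has no grouped count. The stated denominator also understates any second-injection percentage when some subjects do not receive that injection. With one event the size is 10% against 12.5% if eight of 10 are injected, and against 16.7% if six are. The size of the splitting effect depends on how events are coded: in the illustration, three rows of 10% stand in for one of 30%.

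This rests on assumed event counts, on 10 subjects in the analysis set, and on the SAP text available, whose contents list for Section 7 shows no special-interest heading. If every subject receives both injections, the second-injection denominator problem disappears and only the missing grouping remains. The documents show no hidden bleeding signal, and 10 subjects could not establish that injection and biopsy carry similar risk. This is a cheap improvement to the safety report.

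**What to change.** Before database lock, fix a list of PTs that make up procedural bleeding and add one table to SAP 7.2.5:

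- **Rows:** procedural bleeding (grouped) and procedural pain, each with subjects and episodes.
- **Columns:** pre-injection (biopsy), acute first injection and acute second injection periods, as already defined in SAP 4.9.
- **Denominator:** subjects who underwent that procedure. State how subjects biopsied under RMCL-002 are counted in the biopsy column.
- **Anemia:** leave it out of the bleeding group unless it is judged procedure-related, because CKD itself can cause it (Protocol 1.6.5).
- **Comparison with Protocol 1.7.1:** descriptive and like with like only, that is gross hematuria with 3 to 9% and transfusion with less than 1%.
- **Exact confidence intervals:** optional.

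The table uses AE data already collected and changes nothing in the conduct of the trial. The cost is a term list, a little programming, and a grouped rate that will look higher than any single PT line.
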